9.8.1.5 Circulating Tumor DNA Analysis (Plasma) Biomarkers

The presence of cell-free DNA in circulating blood is a well-documented phenomenon. Fragments of DNA are shed into the blood stream from dividing cells during cell proliferation or cell death. In patients with cancer, a fraction of this DNA is tumor-derived and is termed circulating tumor DNA (ctDNA). Albeit small, fragments of DNA average between 180 to 200 bp and specific genomic regions can be amplified with PCR. ctDNA may be a surrogate of disease burden and/or may be used for the assessment of cancer-related gene mutations that may be associated with

response to immunotherapy. Plasma samples may also be used to assess any of the soluble factors described above.

9.8.2 Tumor Samples

Tumor biopsy specimens will be obtained from consenting subjects prior to treatment to characterize immune cell populations and expression of selected tumor markers. A fresh biopsy must be available for submission prior to randomization. Biopsies of bone lesions that do not have a soft tissue component are also unacceptable for submission. On-treatment biopsy samples are optional. Biopsied lesions should be distinct from index lesion(s) being evaluated for radiological response, if clinically feasible.

9.8.2.1 LAG-3 and PD-L1 Expression

Entry to this study is limited to subjects assessed for LAG-3 and PD-L1 expression in tumor specimens. LAG-3 and PD-L1 expression on immune cells will be measured using an analytically validated immunohistochemical assay. LAG-3 and PD-L1 status, as determined using a 1% threshold, will be stratification criteria for randomization.

9.8.2.2 Characterization of Tumor Infiltrating Lymphocytes (TILs) and Immune Biomarkers

Immunohistochemistry (IHC) or other technologies will also be used to assess the number and composition of immune infiltrates in order to define the immune cell subsets present within FFPE tumor tissue before and after exposure to therapy. These IHC analyses will include, but not necessarily be limited to, the following markers: CD8, MHC-I, MHC-II, and PD-L1.

9.8.2.3 Characterization of T-Cell Repertoire

DNA or RNA sequencing may be performed on pre-and post-treatment tumor tissue to assess the composition of the T-cell repertoire. DNA/RNA will be isolated from either the FFPE tumor block or equivalent preparations.

9.8.2.4 Gene Expression Profiling

Tumor biopsies may be examined for mRNA gene expression by RNAseq, EdgeSeq and/or equivalent technology platforms to measure the tumor transcriptome, including genes or gene signatures of interest. These include expression of LAG-3, PD1, and PD-L2 as well as inflammation gene signatures.

9.8.2.5 Tumor Genotyping, Mutational Analysis, and Tumor Antigen Profiling

DNA from tumor samples will be analyzed using whole-exome and transcriptome sequencing to determine the number of mutations found within a given sample relative to a normal host tissue, such as adjacent non-transformed cells, whole blood or PBMC. Mutations that are detected will be analyzed for their ability to bind the MHC I and MHC II proteins using prediction algorithms, such as NetMHC. Evaluating the ability of tumor mutations to bind MHC molecules will provide evidence that these mutations are serving as antigens that are recognized the immune system and are potential rejection antigens.

9.8.2.6 Tumor Sample Collection

The investigator, in consultation with the radiology staff, must determine the degree of risk associated with the procedure and find it acceptable. Biopsies may be done with local anesthesia or conscious sedation. Biopsied lesions should be distinct from index lesion(s) being evaluated for radiological response, if clinically feasible. Institutional guidelines for the safe performance of biopsies should be followed. Excisional biopsies may be performed to obtain tumor biopsy samples. Invasive procedures that require general anesthesia should not be performed to obtain a biopsy specimen. However, if a surgical procedure is performed for a clinical indication, excess tumor tissue may be used for research purposes with the consent of the subject.

Detailed instructions of the obtaining, processing, labeling, handling, storage and shipment of specimens will be provided in a separate Procedure Manual at the time of study initiation

Table 9.8.2.6-1: CA224047 Biomarker Sampling Schedule (All subjects)^a

Collection Timing	Serum	Plasma	Whole Blood	PBMC	Tumor
Screening	--	--	--	--	X ^c
Cycle 1 Day 1	X	X	X	X	
Cycle 2 Day 1	X	X	--	X	X ^e
Cycle 3 Day 1	X	--	--	--	--
Upon Progression ^d	X	X	--	--	X ^e

^a Biomarker sampling occurs prior to dosing of study drug and can occur ± 5 days from the scheduled time.

^b Original footnote b has been deleted.

^c Tumor biopsy prior to therapy is mandatory. If a recent archived biopsy, as defined by protocol, is not available at screening, a fresh biopsy will be taken at any point prior to treatment.

^d Samples from subjects that have confirmed progression are optional.

^e Optional biopsies on-treatment and upon progression and may be taken at the discretion of the investigator.

9.8.2.7 Additional Research Collection

This protocol will include residual sample storage for additional research.

For All US Sites

Additional research participation is required for all investigational sites in the U.S.

For All Non-US Sites

Additional research is optional for all study participants, except where retention and/or collection is prohibited by local laws or regulations, ethics committees, or institutional requirements.

This collection for additional research is intended to expand the translational R&D capability at BMS, and will support as yet undefined research aims that will advance our understanding of disease and options for treatment. It may also be used to support health authority requests for analysis, and advancement of pharmacodiagnostic development to better target drugs to the right

patients. This may also include genetic/genomic exploration aimed at exploring disease pathways, progression and response to treatment etc.

Sample Collection and Storage

All requests for access to samples or data for additional research will be vetted through a diverse committee of the study sponsor’s senior leaders in Research and Development (or designee) to ensure the research supports appropriate and well-defined scientific research activities.

PK, residual tumor, plasma, serum, whole blood DNA, whole blood RNA, and PBMC (see [Table 9.8.2.6-1](#)) will be retained for additional research purposes.

Samples kept for future research will be stored at the BMS Biorepository [REDACTED] or an independent, BMS-approved storage vendor.

The manager of these samples will ensure they are properly used throughout their usable life and will destroy the samples at the end of the scheduled storage period, no longer than 15 years after the end of the study or the maximum time allowed by applicable law.

Transfers of samples by research sponsor to third parties will be subject to the recipient’s agreement to establish similar storage procedures.

Samples will be stored in a coded fashion, and no researcher will have access to the key. The key is securely held by the investigator at the clinical site, so there is no direct ability for a researcher to connect a sample to a specific individual.

Further details of sample collection and processing will be provided to the site in the procedure manual.

Table 9.8.2.7-1: Residual Sample Retention for Additional Research Schedule

Sample Type	Time points for which residual samples will be retained
PK	All
Tumor biopsy	All
Plasma	All
Serum	All
Whole blood DNA	All
Whole blood RNA	All
PBMC	All

9.9 Medical Resource Utilization and Health Economics

Health care resource utilization data will be collected for all randomized participants using an internal CRF developed for use in previous trials. The form, which is completed by study staff, records information about hospital admissions, including number of days spent in various wards and discharge diagnosis, as well as non-protocol specified visits related to study therapy, including

date of visit, reason for visit, and type of visit. The health care resource utilization data will be used to support subsequent economic evaluations.

10 STATISTICAL CONSIDERATIONS

10.1 Sample Size Determination

The sample size for the study is based on a primary endpoint of PFS using BICR for either a Phase 2 or a Phase 3 study. The sample size for the Phase 2 study as justified below is approximately 400 randomized participants. The sample size for the Phase 3 study as justified below is 700 randomized participants, comprised of the Phase 2 population and an additional 300 participants.

The overall alpha for the Phase 3 study is 0.05 (two-sided) with detailed alpha-spending strategy described in [Section 10.2.2](#).

Sample Size Justification for Phase 2 PFS Estimation

The primary objective of the Phase 2 portion of the study is to demonstrate preliminary clinical evidence of the treatment effect, measured by PFS, as determined by BICR using RECIST v1.1 in randomized participants with unresectable or metastatic melanoma treated with BMS-986213 compared to those treated with nivolumab monotherapy. The number of events is based on results from study CA209067 with a median PFS of 6.9 months for nivolumab monotherapy and 11.8 months for nivolumab with relatlimab. With 183 events, there will be approximately 80% power to detect a hazard ratio (HR) = 0.73 with a type 1 error of 0.1 (1-sided). The cure rates were assumed to be 30% in the nivolumab arm and 40% in the nivolumab with relatlimab arm. The power is also affected by non-proportional hazards, since it is driven by the number of events, not the number of study participants, and some fraction of the participants in each arm are assumed will remain event-free for the duration of the study. Approximately 400 participants will be randomized to the Phase 2 study to ensure enough power to analyze the biomarker subgroups (see section below on the secondary endpoint of ORR in subgroup).

Based on an anticipated screen failure rate of 30%, approximately 575 participants will need to be screened in order to randomize approximately 400 participants who fit the eligibility criteria.

Sample Size Justification for Phase 3 PFS Comparison

The sample size is calculated in order to compare PFS among participants randomized to receive BMS-986213 versus nivolumab. The number of events required is simulated based on results from study CA209067, with a median PFS of 6.9 months for nivolumab monotherapy and 11.8 months for nivolumab with relatlimab, incorporating 35% of subjects with durable response in the combined groups, and a piecewise hazard ratio resulting in an effective hazard ratio of approximately 0.73.

Based on these assumptions, the study requires 365 PFS events to ensure approximately 85% power to detect a hazard ratio of 0.73 with an overall type I error of 0.05. Approximately 700 participants will be randomized to the two treatment arms in a 1:1 ratio. The final PFS analysis is planned to occur when 365 participants have had a PFS event per BICR. Total enrollment will take approximately 27 months (including a potential 6-month pause due to the interim PFS analysis).

Based on an anticipated screen failure rate of 30%, approximately 1000 participants will need to be screened in order to randomize 700 participants who meet the eligibility criteria.

Sample Size Justification for Secondary Objective of Overall Survival Comparison in Phase 3 Trial

The sample size is calculated in order to compare OS among participants randomized to receive BMS-986213 versus nivolumab. The number of OS events (deaths) required is based on results from study CA209067, with a median PFS of 36.9 months for nivolumab monotherapy and 49.2 months for nivolumab with relatlimab, resulting in an effective hazard ratio of approximately 0.75. With 300 deaths the power will be approximately 69% with a type I error rate of 0.05.

Sample Size Justification for Secondary Objective of Subgroup Comparison in Phase 2 Trial

If the interim PFS analysis does not support continuing to a Phase 3 study, the study will complete as a Phase 2 trial. The primary objective of the Phase 2 study using patients with previously untreated, unresectable or metastatic melanoma is to assess preliminary clinical evidence of the treatment effect measured by PFS as determined by BICR that may represent substantial improvement over available therapies. As a secondary objective, the Phase 2 will examine ORR information in biomarker subgroups based on LAG-3 expression ($\geq 1\%$ expression versus $< 1\%$ expression) and PDL-1 status ($\geq 1\%$ tumor cell surface expression versus $< 1\%$ tumor cell surface expression). ORR information and biomarker prevalence rates (for LAG-3 positive and negative expression, and for PDL-1 positive and negative status) used in the sample size calculations were based on information from study CA209067 and interim information from study CA224020. Table 10.1-1 shows the power for varying ORRs and varying prevalence rates for subgroups, assuming a Type 1 error rate of 0.1 (one-sided) and an overall N of 400 subjects. The Benjamini-Hochberg procedure will be used to control the False Discovery Rate (FDR) when testing multiple subgroups.

Table 10.1-1: Power for Subgroups with Different N and Prevalence

Overall N for Phase 2 Study	Subgroup N	Subgroup ORR	Subgroup Prevalence	Power (one-sided alpha .1 and 20% delta)
400	200	0.7	0.5	0.991
	140	0.7	0.35	0.962
	50	0.5	0.125	0.576
	80	0.5	0.2	0.72
	50	0.33	0.125	0.57
	80	0.33	0.2	0.713
	100	0.23	0.25	0.815
	120	.23	0.3	0.865

Populations for Analyses

For purposes of analysis, the following populations are defined:

Population	Description
Enrolled Participants	All participants who sign informed consent and were registered into IRT
Randomized	All participants who are randomized to any treatment group.
Treated	All participants who received at least one dose of double-blind study medication.

Population	Description
Safety	All randomized participants who take at least 1 dose of double blind study treatment. Data in this data set will be analyzed based on randomized treatment, except in the following cases: 
 • If a participant received the same incorrect treatment throughout the study, then the participant will be analyzed based on the treatment received. • If a participant received study drug from more than one treatment group, and none of the administrations were consistent with the assigned randomized treatment group, then the participant will be analyzed based on the first treatment received.
PK	All randomized participants with available serum time-concentration data.
Immunogenicity	All randomized participants with available ADA data.
Biomarker	All randomized participants with available biomarker data.

10.2 Statistical Analyses

10.2.1 Demographics and Baseline Characteristics

Frequency distributions of gender, race, ethnicity, and other categorical baseline characteristics will be tabulated. Baseline body mass index (BMI) will be derived from measurements of baseline body weight and height. Summary statistics for age, body weight, height, and BMI will be tabulated. Baseline disease characteristics will be summarized for expansion cohorts for different disease cohorts separately, as appropriate.

10.2.2 Efficacy Analyses

Below is a summary of planned statistical analyses of the primary and secondary efficacy endpoints.

Endpoint	Statistical Analysis Methods
Phase 3 Primary	
PFS time, as assessed by a BICR, using RECIST v1.1. PFS is defined as the time between the date of randomization and the first date of documented progression, or death due to any cause, whichever occurs first.	Two-sided log-rank test stratified by LAG-3 expression ($\geq 1\%$ vs $< 1\%$), (PD-L1 status ($\geq 1\%$ vs $< 1\%$), BRAF status, and AJCC (8th edition) M Stage in randomized participants to compare the PFS of relatlimab + nivolumab arm (BMS-986213) and the nivolumab alone arm. Hazard ratios and corresponding 2-sided 95% CI will be estimated using a Cox proportional hazards model, with

Endpoint	Statistical Analysis Methods
	
treatment group as a single covariate, stratified by the above factors.
 
PFS curves, PFS medians with 95% CIs, and PFS rates at 6 and 12 months with 95% CIs will be estimated using Kaplan-Meier methodology.

Phase 3 Secondary	

OS time is defined as the time between the date of randomization and the date of death due to any cause.
	
This test will only be interpreted if the primary analysis is significantly superior. Two-sided log-rank test stratified by LAG-3 expression ($\geq 1\%$ vs $< 1\%$), PD-L1 status ($\geq 1\%$ vs $< 1\%$), BRAF status, and AJCC (8th edition) M Stage will be used to compare the relatlimab + nivolumab arm (BMS-986213) and the nivolumab arm. Hazard ratio and corresponding two-sided 95% CI will be estimated using a Cox proportional hazards model, with treatment group as a single covariate, stratified by the above factors. Additionally, OS curves, OS medians with 95% CIs, and OS rates at 12 months with 95% CIs will be estimated using Kaplan-Meier methodology.


ORR as assessed by BICR. The ORR is defined as the number of subjects with a BOR of CR or PR divided by the number of randomized subjects for each treatment group. The BOR is defined as the best response designation, recorded between the date of randomization and the date of objectively documented progression per RECIST v1.1 or the date of subsequent anti-cancer therapy, whichever occurs first.
	
This test will only be interpreted if the primary (PFS) and first secondary (OS) analyses are significantly superior. Two-sided Cochran-Mantel-Haenszel (CMH) test stratified by LAG-3 expression ($\geq 1\%$ vs $< 1\%$), (PD-L1 status ($\geq 1\%$ vs $< 1\%$), BRAF status, and AJCC (8th edition) M Stage to compare the BMS-986213 arm and the nivolumab monotherapy arm. Associated odds ratios and 95% CIs will be calculated. Additionally, ORRs and corresponding 95% exact CIs will be calculated using the Clopper Pearson method.

Phase 3 Exploratory	
Will be described in the Statistical Analysis Plan (SAP) finalized before database lock

Phase 2 Primary	

PFS time, as assessed by BICR, using RECIST v1.1. PFS time is defined as the time between the date of randomization and the first date of documented
	
Two-sided log-rank test stratified by LAG-3 expression ($\geq 1\%$ vs $< 1\%$), (PD-L1 status ($\geq 1\%$ vs $< 1\%$), BRAF status, and AJCC (8th edition) M Stage in randomized participants to compare the PFS of relatlimab + nivolumab arm (BMS-986213) and the

Endpoint	Statistical Analysis Methods
progression, or death due to any cause, whichever occurs first.	nivolumab alone arm. Hazard ratios and corresponding 2-sided 95% CI will be estimated using a Cox proportional hazards model, with treatment group as a single covariate, stratified by the above factors. PFS curves, PFS medians with 95% CIs, and PFS rates at 6 and 12 months with 95% CIs will be estimated using Kaplan-Meier methodology.
Phase 2 Secondary	
ORR as assessed by BICR.	Summary of ORR with corresponding 2-sided 95% CI in each arm and for the difference between arms, along with each category of BOR. Multiple comparisons in population subgroups will be handled using the Benjamini-Hochberg method to control the False Discovery Rate (FDR) at 0.05.
DOR is defined as the time between the date of first response to the date of first documented tumor progression (per RECIST v1.1) or death due to any cause. TTR is defined as the time from randomization to the date of the first documented CR or PR.	Summary of DOR with median (95% CI) and range (min, max) by K-M method. Summary of median Time to Response (mTTR) (95% CI)
PFS time and PFS rate as assessed by BICR, using RECIST v1.1 for subgroups	Summary of PFS with median (95% CI) by Kaplan-Meier method and PFS rate
OS is defined as the time between the date of randomization and the date of death due to any cause.	OS with median (95% CI) and range (min, max) by Kaplan-Meier method
Phase 2 Exploratory	Will be described in the SAP finalized before database lock

PFS is defined as the time between the date of randomization and the first date of documented progression, or death due to any cause, whichever occurs first. Participants who die without a reported progression will be considered to have progressed on the date of their death. Participants who did not progress or die will be censored on the date of their last evaluable tumor assessment. Participants who did not have any on study tumor assessments and did not die will be censored on their date of randomization. Participants who started anti-cancer therapy without a prior reported

progression will be censored on the date of their last evaluable tumor assessment prior to the initiation of subsequent anti-cancer therapy.

Phase 3 Testing Strategy

The Phase 2 part of the study will enroll approximately 400 participants. An interim analysis of PFS will be performed when a minimum follow-up of 12 weeks is achieved for approximately 400 randomized subjects or at least 150 PFS events have been observed using BICR.

- If the interim PFS analysis achieves the pre-specified threshold (as defined in the SAP and the DMC Charter), then the study will continue to Phase 3 and remain blinded.
- If interim PFS analysis does not achieve the pre-specified threshold (as defined in the SAP and DMC Charter) the study will not open enrollment to Phase 3. The Phase 2 data will be allowed to mature and then the sponsor will unblind for analysis. If that scenario takes place, approximately 575 participants will need to be enrolled in order to randomize 400 participants assuming a screen failure rate of 30%.

The overall alpha for the Phase 3 study is 0.05 (two-sided).

For the Phase 3 study, type I error control across endpoints will be performed hierarchically. The primary analysis is for PFS. If that analysis is significantly superior, then the secondary endpoints may be tested in the order of OS followed by ORR. That is, if the results comparing PFS between treatment groups are significant at the applicable alpha level, then results comparing OS between treatment groups will be interpreted. If the results comparing OS between treatment groups are significant, then results comparing ORR between treatment groups will be interpreted. Other endpoints will not be tested formally.

An administrative alpha penalty of 0.001 will be used for the interim PFS analysis. If the interim PFS analysis meets the pre-specified threshold and proceeds to Phase 3, the final PFS analysis will be performed when approximately 365 PFS events have occurred per BICR and will use all remaining unspent alpha. If the pre-specified efficacy boundary is achieved at PFS final analysis, all remaining alpha will be passed to OS in a hierarchical fashion as described above, and participants will continue to be followed for OS.

Assuming the PFS result is significantly superior (at the final PFS analysis), there will be interim analyses of OS. The interim OS analyses will use an O'Brien-Fleming boundary based on the actual number of deaths observed. The first interim analysis of OS (OS IA1) will take place at the same time as final PFS. If OS IA1 does not achieve statistical significance, the second interim analysis of OS (OS IA2) will be performed when a minimum of 90% (270/300) of the expected deaths have occurred. If OS IA2 is not statistically significant, the final OS analysis will be performed when approximately 300 deaths have occurred.

If PFS and OS are each significantly superior, then ORR will be formally tested.

Phase 2 Testing Strategy

If the interim PFS analysis indicates the study will stop at Phase 2 the study will not enroll any additional participants, and the study will remain blinded until the data are sufficiently mature (183 PFS events and a minimum 6 months of follow-up). The final Phase 2 analysis includes multiple subgroups of interest. The Benjamini-Hochberg method will be used to account for multiplicity by controlling the False Discovery Rate (FDR) when making comparisons in multiple subgroups.

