5.2 Number of Participants

The Phase 2 part of the study will enroll approximately 400 participants. An interim analysis will be performed when a minimum follow-up of 12 weeks is achieved for approximately 400 randomized subjects or at least 150 PFS events have been observed using BICR. The interim PFS analysis is a futility analysis. If the interim PFS analysis is positive (based on the pre-specified threshold as defined in the Statistical Analysis Plan [SAP]), then the study will continue to Phase 3 and remain blinded. If the interim PFS analysis does not support continuing to the Phase 3 study,

the study will allow the Phase 2 data to mature and then unblind the sponsor for analysis. If the latter scenario takes place, approximately 575 participants will need to be enrolled in order to randomize 400 participants assuming a screen failure rate of 30%.

If the study does continue to Phase 3, it is expected that approximately 1000 participants will need to be enrolled to randomize at least 700 participants, assuming a screen failure rate of approximately 30%.

Participants will be randomized 1:1 to one of two parallel treatment groups:

- BMS-986213 by intravenous (IV) infusion every 4 weeks (Q4W)
- nivolumab IV Q4W

See [Section 10.1](#) for sample size determination.

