**Table 5.1.2-1: Power for Subgroups with Different N and Prevalence**

Overall N for Phase 2 Study	Subgroup N	Subgroup ORR	Subgroup Prevalence	Power (one-sided alpha .1 and 20% delta)
400	200	0.7	0.5	0.991
	140	0.7	0.35	0.962
	50	0.5	0.125	0.576
	80	0.5	0.2	0.72
	50	0.33	0.125	0.57
	80	0.33	0.2	0.713
	100	0.23	0.25	0.815
	120	.23	0.3	0.865

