### **7.5 Efficacy**

Below is a brief summary table (Table 7.5-1) of planned statistical analyses of the primary and secondary efficacy endpoints. Following the summary table are more details about each analysis in individual sections.

Unless stated otherwise, whenever a stratified analysis is specified, the following stratification factors will be used PD-L1, LAG-3, BRAF, AJCC M Stage. Each of the 4 stratification factors has 2 levels, with 16 strata in total. Anticipating the study population may not be equally distributed across levels in a given stratification factor, it is likely that the number of subjects in some strata may be small. With 2 treatment arms in this study, the stratum size with less than 10 subjects would likely cause unreliable estimates in the stratified analyses Therefore, in the case of less than 10 subjects in a strata or in the case of unexpected model convergence issues due to small strata with too small event numbers, stratification factors would be removed one at a time from the model until convergence is achieved. This will happen in the following order: (1) PD-L1 and (2) the stratification factor with the lowest prevalence in a level. A sensitivity analysis of PFS will be performed using the original stratification variables as per IRT.

- PD-L1 Expression: PD-L1 $\geq$ 1% tumor cell surface expression vs PD-L1 $<$ 1% tumor cell surface expression/ non-quantifiable (from LabCorp LA)
- LAG-3 Status: LAG-3 $\geq$ 1% expression vs LAG-3 $<$ 1% expression (from IRT)
- BRAF Status: Mutation Positive/ vs Mutation Wild-type (from IRT)
- AJCC M Stage: M0/M1any[0] vs M1any[1] (from lab value and eCRF)

All p-values reported will be two-sided.

CI's for the efficacy endpoints will be at the two-sided 95% level. The p-values presented in the CSR will be rounded to the fourth decimal place. Point estimates and confidence bounds for efficacy variables will be rounded to the second decimal place.

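### The Phase 2 subgroup ORR power table assumes unadjusted tests at one-sided 0.1, but the plan tests the subgroups by Benjamini-Hochberg at FDR 0.05, so every row overstates the power of the planned analysis

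*Protocol*

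**What the plan says.** **Role of the table.** After the 183-event PFS calculation, Protocol 10.1 gives the reason for the Phase 2 sample size: "Approximately 400 participants will be randomized to the Phase 2 study to ensure enough power to analyze the biomarker subgroups". It points the reader to the ORR subgroup section.

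**Power basis.** That section computes power "assuming a Type 1 error rate of 0.1 (one-sided) and an overall N of 400 subjects". The column header, the same in the SAP, reads "Power (one-sided alpha .1 and 20% delta)". Directly before the table the Protocol adds: "The Benjamini-Hochberg procedure will be used to control the False Discovery Rate (FDR) when testing multiple subgroups". No FDR level is given there.

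**Analysis rule.** The level appears in the Phase 2 secondary ORR row of Protocol 10.2.2, repeated in SAP Table 7.5-1: "Multiple comparisons in population subgroups will be handled using the Benjamini-Hochberg method to control the False Discovery Rate (FDR) at 0.05". That row does not name the test that produces the p-values.

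**Sidedness.** SAP 7.5 says "All p-values reported will be two-sided". Neither document says separately which p-values enter the Benjamini-Hochberg procedure, or how many hypotheses it covers.

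**The concern.** The test that was powered is not the test that is planned. The table uses a fixed one-sided 0.1 cutoff in each subgroup taken alone. Benjamini-Hochberg over m subgroups at level 0.05 rejects the hypotheses with the k smallest p-values, where k is the largest rank whose ordered p-value is at most k × 0.05/m. The most lenient cutoff it can reach is 0.05, when all m are rejected. That is half the tabulated level with one-sided p-values, and a quarter of it (one-sided 0.025) with two-sided p-values.

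The table is the documents' stated reason for enrolling 400 in Phase 2. Had the study stopped there, it would also have shaped how a negative subgroup result was read: a reader would credit an 80-patient subgroup at ORR 0.5 with 72% power when the planned procedure offers less.

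**Working it through.** **Inputs.** Subgroup N, control ORR and stated power come from Protocol Table 10.1-1. The effect is 20 percentage points. Allocation is 1:1 (Protocol 5.2), so n = N/2 per arm.

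**Step 1: reproduce the table.** Use the two-proportion z test with unpooled variance, with p1 the tabulated ORR and p2 = p1 + 0.20:

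power = Φ( 0.20 / √[(p1(1−p1) + p2(1−p2))/n] − z )

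with z = 1.2816 for one-sided 0.1. For N=50 at ORR 0.5: variance (0.25 + 0.21)/25 = 0.0184; standard error 0.1356; 0.20/0.1356 = 1.474; Φ(1.474 − 1.2816) = 0.576, as stated. All eight rows match to three decimals, so the table contains no multiplicity adjustment.

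**Step 2: ceiling under Benjamini-Hochberg at 0.05.** Keep the formula and replace z by 1.6449 (one-sided p ≤ 0.05) or 1.9600 (two-sided p ≤ 0.05). For the same row: Φ(1.474 − 1.6449) = 0.432 and Φ(1.474 − 1.9600) = 0.314.

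| N | ORR | Stated | Ceiling, one-sided p | Loss (points) | Ceiling, two-sided p | Loss (points) |
|---|---|---|---|---|---|---|
| 200 | 0.70 | 0.991 | 0.978 | 1.3 | 0.955 | 3.6 |
| 140 | 0.70 | 0.962 | 0.921 | 4.1 | 0.863 | 9.9 |
| 50 | 0.50 | 0.576 | 0.432 | 14.4 | 0.314 | 26.2 |
| 80 | 0.50 | 0.72 | 0.587 | 13.3 | 0.462 | 25.8 |
| 50 | 0.33 | 0.57 | 0.426 | 14.4 | 0.308 | 26.2 |
| 80 | 0.33 | 0.713 | 0.579 | 13.4 | 0.454 | 25.9 |
| 100 | 0.23 | 0.815 | 0.703 | 11.2 | 0.586 | 22.9 |
| 120 | 0.23 | 0.865 | 0.770 | 9.5 | 0.664 | 20.1 |

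These ceilings hold for any m, because no Benjamini-Hochberg rejection at 0.05 can have p above 0.05.

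**Step 3: illustration under an assumed m.** Assume m = 4 disjoint subgroups, in the sets {200, 50, 50, 100} and {140, 80, 80, 100}, a true 20-point effect in all four, and two-sided p-values. Simulated Benjamini-Hochberg power is about 0.92 (N=200), 0.80 (N=140), 0.26 to 0.29 (N=50, ORR 0.5), 0.40 (N=80, ORR 0.5) and 0.50 to 0.52 (N=100). The ranges reflect the choice of test statistic. With the effect in one subgroup only, the values fall to about 0.88, 0.72, 0.16 to 0.19, 0.27 to 0.29 and 0.38 to 0.40.

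**Step 4: would raising the FDR level to 0.1 reconcile them?** No. The one-sided 0.1 cutoff is then reached only when every hypothesis is rejected. For the set 140 (ORR 0.70), 50 (0.50), 80 (0.33) and 120 (0.23), with all four effective and one-sided p-values, simulated power at FDR 0.1 is 0.945, 0.536, 0.666 and 0.824, against stated 0.962, 0.576, 0.713 and 0.865.

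**The case against.** The strongest reply is that the table is not miscalculated. Each value is right for the test named in its header, the level is disclosed, and the sentence before the table announces Benjamini-Hochberg. The documents never claim that the column is power under that procedure. This stands as far as it goes: the fault is a mismatch between planning level and analysis rule, and a reader who inferred a computational error would be wrong. It does not rescue the use of the table, because Protocol 10.1 relies on it for power to analyse these same subgroups.

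The second reply is that little turns on it, and this stands. The comparison belongs to the branch in which the study stops at Phase 2. SAP 5 records that the study proceeded to Phase 3 on 26AUG2019. Phase 3 formally tests only PFS, OS and ORR, and biomarker subgroup efficacy there is exploratory.

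The third reply concerns inputs, and it also stands. A reader might infer that the prevalences prove m = 4, since 0.5 + 0.125 + 0.125 + 0.25 = 1 and 0.35 + 0.2 + 0.2 + 0.25 = 1. But the second sum reuses the 0.25 row and leaves out the 0.3 row; with 0.3 it is 1.05. The Phase 2 ORR objective also names all-comers. Four is plausible for two binary markers, but it is not stated. Nor does the SAP's rule on reported p-values settle which p-values enter Benjamini-Hochberg, since Phase 2 planning is one-sided.

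**Conclusion.** The point holds. Every row of the table overstates power for the planned analysis, whatever m and whichever sidedness. The certain loss, under the most favourable reading, is 1.3 to 14.4 points by row. With two-sided p-values it is at least 3.6 to 26.2 points. Both ranges assume the same unpooled z test that reproduces the table.

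Two stronger readings go too far. A reader might conclude that the N=50 subgroups really have about 15 to 40% power instead of 57%. Such figures depend on an assumed m, sidedness and number of truly effective subgroups; without those assumptions, one can say only that power is at most 43%. A reader might also conclude that 400 was too few. The documents set no subgroup power target, the table openly runs from 0.57 to 0.99, and SAP 5 gives the Phase 2 part other purposes (the decision to continue, and patients for Phase 3).

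Severity is low. This is a design-stage power statement in a branch that was not taken. PFS power at 183 or 365 events does not rest on it.

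**What to change.** Either recompute Protocol Table 10.1-1 and SAP Table 5.1.2-1 under the stated Benjamini-Hochberg procedure, giving the number of hypotheses, the sidedness of the p-values and the assumed pattern of true effects; or label the present column as unadjusted, per subgroup, and add a Benjamini-Hochberg column beside it.

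If a screening-level FDR was intended, state that level in Protocol 10.2.2 and SAP Table 7.5-1 and still recompute the table at that level. Changing the level alone does not bring test and table into agreement (step 4 of the working).

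The cost is one recalculated table and a sentence in each document. The figures become less favourable. Patients, data and Phase 3 testing are unaffected.
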